Group 1: Oral and enema FMT, Group 2: Oral FMT+ enema placebo, Group 3: Oral placebo + enema FMT, Group 4: Both placebo *Visit 2* After re-confirming eligibility, the patient will be seen within 3±5 days of visit 1. Vital signs and weight will be measured. Targeted physical exam will be done based on any symptoms.

Their symptom diaries and dietary recall will be examined. Stool, blood and urine will be collected and processed (see section below), including urine

pregnancy testing for women of child-bearing potential. After this we will administer the assigned intervention by enema and oral capsules. This has been tolerated without any issues in our current protocols. These will be dispensed from our VAMC Investigational Pharmacy, which has been handling these for our prior and current FMT trials. The

following will be recorded in all FMTs (dose, Unit ID/Lot# of each treatment, Expiration Date and storage condition) The patient will be observed for a further 1 hour and then given another stool kit to bring back 10±5 days from this visit (Visit 3). All subjects will be given contact information for the study team to call in case any issues arise.

Optionally, subjects may elect to combine Visits 1 and 2 to minimize potential COVID exposure. In this case, stool collection kit would be mailed to subject before visit, and the staff would provide further instructions to subject on their use. The subject may determine whether he/she will collect a stool sample to bring to the study clinic visit. In the event the subject decides not to participate in the study, the stool collection kit would be discarded.

Visit 3: We will see the patient in the McGuire VAMC at day 15, at which point, dietary recall will again be performed along with changes in GI or other adverse events using interview and review of the symptom diaries. If no adverse event (AE) or serious adverse events (SAE) occur (standard definitions and in the human subjects protection section per FDA specifications), the subject will continue in the study. Vital signs and weight will be measured. Targeted physical exam will be done based on any symptoms. The stool sample, blood and urine will be collected for microbiota and safety analysis. Changes in blood counts that prompt attention (MELD score increase by 8, WBC count change to >13,000 or <2,000) will be monitored. If all is well, then subjects will be discharged with another stool kit and instructions for the last visit 15±3 days later (visit 4).

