Visit 4: All procedures as in visit 2 will be performed again, including dietary recall, targeted physical exam, and sample collection. All subjects will also get another oral FMT/placebo dose of 5 capsules each depending on their original assignment. All subjects in the study will get this intervention unless (a) they refuse the intervention (b) have undergone a liver transplant or have died/discharged to hospice (c) developed an infection or an SAE that was adjudicated to be related to FMT in the interim or (d) are currently undergoing antibiotic therapy for an infection that is not related to FMT.

For those who are infected due to an FMT-unrelated infection, we will approach the patients 2 days after the completion of the assigned antibiotic course. For those initiated on SBP (Spontaneous Bacterial Peritonitis) prophylaxis, we will provide the intervention after the initial SBP episode is treated. This may require delaying the intervention from day 30 to up to day 45 but this will still be counted as the second FMT.

All other subjects will be given the intervention and the blind will still be maintained. The brain function tests and QOL will be performed again. Groups 1 and 2 will get active FMT and groups 3 and 4 will get placebo FMT. No enemas will be given. The subjects will then be sent home.

Follow-up visits every month: The subjects will be followed monthly in person, or by phone or videoconference at Months 3, 4, 5 to evaluate dietary and medication changes and for safety analysis (hospitalizations, AEs or SAEs), targeted physical exam and for collection of samples at each study clinic visit. Mail-in kits for collection of stool, and urine will be provided along with instructions for use if visit is performed remotely. We will also perform the cognitive tests and QOL assessment at one month post-second intervention and at 6 months. We will continue to follow every patient for 6 months regardless of whether they developed an SAE or hospitalization in between. Only reasons not to follow them up for 6 months would be death, liver transplantation or patient withdrawal of consent.

End-of-Study visit: Per FDA mandates for FMT studies, we will see the patients at six months and we will evaluate AEs, interim hospitalizations, dietary recall, and perform targeted physical exam, QOL and brain function studies, and collect serum, and stool again. At this point the participation of the patient will end.

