Specific safety findings will result in temporarily suspending enrollment until a safety review is convened, the objective of which is to determine whether the study should continue per protocol, proceed with caution, be further investigated, be discontinued, or be modified and then proceed. Suspension of enrollment is another potential outcome of a safety review. This will be done if the assigned infection is in the FMT group since this patient population is prone to infections.

Subsequent review of serious, unexpected, and related AEs by the Data and Safety Monitoring Board, IRB, the PI, or the FDA or relevant local regulatory authorities may also result in suspension of further trial interventions/administration of FMT at a site. The FDA and PI retain the authority to suspend additional enrollment and study interventions/administration of FMT for the entire study, as applicable. The PI and the adjudication panel will make the initial decision. The subsequent safety review by the IRB and FDA will then decide if the study can resume.

Findings that will trigger a safety review are

Findings that will trigger a safety review are

- o Death related to FMT material or study procedures in any subject;
- New potentially transmitted infection in five or more subjects assigned to FMT - i.e., cannot exdude transmission and/or attribution is

pending investigation/Data Monitoring Committee (DMC) adjudication;

- Any single potential transmitted infection assessed as possibly, probably, or definitely related to FMT by the investigator and DMC.
- One or more subjects assigned to FMT has a serious, unexpected AE assessed as possibly, probably, or definitely related to FMT by the investigator and DMC; Five or more subjects (per assigned group) develop a new diagnosis of a medical condition or immune-mediated disease considered probably, or definitely related to FMT.
- Five or more severe AEs of a similar nature occurring in different subjects and assessed as definite, possible or probable relatedness to study product in groups assigned to FMT (per assigned group)

FDA/CBER will be notified by phone or fax within 72 hours if the study is halted for review.

Individual study halting rules

- (1) patient's choice
- (2) change in GI adverse events with a magnitude of 3 increase over baseline
- (3) fever and signs of infection (including WBC count >12,000/ml)
- (4) SAE development including cirrhosis complications (OHE) and hospitalizations for

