- any cause including bleeding, nausea, vomiting, or other GI conditions
- (5) increase in MELD score by 8 or more
- (6) Increase in AST, ALT or Alkaline phosphatase to 10X ULN
- (7) Non-elective Hospitalization

Even if the subject is withdrawn before 30 days, they will still be followed till 6 months for safety.

Health risks (please see adverse events table attached):

Adverse events will be both for the FMT material, placebo as well as for the procedures. These risks are listed in the Risk Section of the informed consent.

These possible adverse events will be:

- (a) Fever: yes or no answer with grading based on actual temperature on examination
- (b) diarrhea (will be asked to grade them from 0-4 compared to baseline)
- (c) abdominal cramping and pain (will be asked to grade them from 0-4 compared to baseline)
- (d) vomiting (will be asked to grade them from 0-4 compared to baseline)
- (e) Development of HE (Altered mental status) in every group: will be monitored by clinical examination through the West-Haven Criteria²⁵. We will be closely monitoring all subjects for this development, including a clinical examination by a gastroenterologist at every visit.

(f) Development of infections specifically spontaneous bacterial peritonitis -Fever will be reconfirmed by measuring by the study nurse and if it is confirmed, a detailed investigation into the cause of the fever will be performed as part of standard clinical care and the patient will be withdrawn from the study.

-Vomiting, constipation, GI bleeding, abdominal cramps and diarrhea: If the patient's diarrhea and abdominal cramps change in a magnitude of 3 over their baseline values per the AE chart (patients with cirrhosis often have these symptoms at baseline), they will be withdrawn from the study.

-Infections that occur in the FMT group will be thoroughly investigated according to standard clinical care to prove whether they were associated with the FMT.

Adverse Event Grading Chart

 Volunteer Study ID:
 Date:
 Time:

 Study Start Date:
 Current Visit number:

*Volunteer's responses will be marked on grading sheet by circling the appropriate grade or indicating no symptoms.

PARAMETER COMPARED TO BASELINE	GRADE 1 MILD	GRADE 2 MODERATE	GRADE 3 SEVERE	GRADE 4 POTENTIALLY LIFE-THREATENING
ESTIMATING SEVERITY	(GRADE		•	•

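### After an FMT-unrelated event before day 30, the individual halting rules stop the subject while Visit 4 gives the second capsule dose, and no text says which governs

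*Combined protocol and SAP*

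**What the plan says.** **Individual study halting rules.** Rule 4 reads "SAE development including cirrhosis complications (OHE) and hospitalizations for" and continues "any cause including bleeding, nausea, vomiting, or other GI conditions". Rule 7 is non-elective hospitalization. Rule 3 is fever and signs of infection, including a raised WBC count. Rules 2, 5 and 6 are a GI change of 3 over baseline, a MELD rise of 8 or more, and AST, ALT or alkaline phosphatase at 10 times ULN. None carries a relatedness condition. The list closes with "Even if the subject is withdrawn before 30 days, they will still be followed till 6 months for safety".

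**Health risks.** Confirmed fever is investigated as part of "standard clinical care and the patient will be withdrawn from the study". Diarrhea and abdominal cramps that change by 3 over baseline lead to the same withdrawal.

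**Procedures, Visit 4.** The day-30 capsules follow a different rule: "All subjects in the study will get this intervention unless" one of four exceptions applies. These are (a) refusal; (b) transplant, death or hospice; (c) the subject "developed an infection or an SAE that was adjudicated to be related to FMT in the interim"; or (d) the subject is among those who "are currently undergoing antibiotic therapy for an infection that is not related to FMT". Exception (d) only defers the dose. The subject is approached 2 days after the antibiotic course ends, or dosed once an SBP episode has been treated, with delay possible to day 45. Visit 4 then says that all other subjects are dosed.

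**The concern.** The two sections give opposite instructions for the same subject, and nothing ranks them. The events concerned are not remote: OHE and hospitalization are what the trial expects to see in this population, and the sample size rests on hospitalization.

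Two things are at stake. The first is dosing: whether a subject with an unrelated early event gets the second dose depends on which page the site follows. The second is safety: a site working only from the Visit 4 list would dose a subject whose MELD had risen by 8, whose enzymes had reached 10 times ULN, or whose GI symptoms had changed by 3. The halting section treats each of these as a reason to stop.

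**Working it through.** The plan states no figure on this point, so the main check is a comparison of texts. Counts are for scale only.

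**1. The rules side by side.** The events below occur before day 30. The first five are taken as not FMT-related, with no other Visit 4 exception applying.

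| Event | Halting rules / Health risks | Visit 4 |
|---|---|---|
| Non-infectious SAE, OHE or non-elective admission | Stop (4, 7) | Dose |
| Fever with signs of infection, on antibiotics | Stop (3, fever withdrawal) | Defer, then dose |
| GI change of 3 | Stop (2) | Not listed: dose |
| MELD rise of 8 or more | Stop (5) | Not listed: dose |
| Enzymes at 10 times ULN | Stop (6) | Not listed: dose |
| SAE adjudicated FMT-related | Stop (4) | Withhold (c) |
| Refusal | Stop (1) | Withhold (a) |

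The rules agree in the last two rows and conflict in the first five.

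**2. Could the Visit 4 population already exclude halted subjects?** If so, any SAE would have removed the subject before Visit 4, and the relatedness test in (c) would do no work for SAEs. The provisions for dosing after an unrelated infection or a treated SBP episode would also largely contradict rules 3, 4 and 7. This reading does not reconcile the texts.

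**3. Does the Safety and hospitalization analysis section add a relatedness condition to the halting rules?** Its stopping rules follow a DMC vote of relatedness that goes to the FDA and the supplier, which fits the study-level rules better. It also covers only SAEs or deaths in FMT-randomized groups, so it cannot settle the matter for Group 4.

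**4. Scale.** Inputs from Sample size: 25 per group, and 6-month hospitalization p of 10% (Group 1, dual), 30% (Groups 2 and 3, single route) and 80% (Group 4; the plan's standard-of-care rate). The documents give no event timing, so three assumed forms are used for the risk by day 30 of 180:

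- linear: p × 30/180
- constant hazard: 1 − (1 − p)^(30/180)
- rising hazard (Weibull, shape 1.5): 1 − (1 − p)^((30/180)^1.5). Exclusion G, which bars a non-elective admission in the prior month, makes a lower early risk plausible.

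| | Linear | Constant | Rising |
|---|---|---|---|
| p = 0.1 | 1.7% | 1.7% | 0.7% |
| p = 0.3 | 5.0% | 5.8% | 2.4% |
| p = 0.8 | 13.3% | 23.5% | 10.4% |
| Active capsules, Groups 1+2: 25 × (r0.1 + r0.3), of 50 | 1.67 | 1.88 | 0.78 |
| Placebo capsules, Groups 3+4: 25 × (r0.3 + r0.8), of 50 | 4.58 | 7.32 | 3.19 |
| Total of 100 | 6.25 | 9.20 | 3.97 |

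Here r is the day-30 risk for that p. If the 80% was 8 of 10 (assumed from the group size in the enema-trial table), its exact 95% interval is 44.4% to 97.5%. The Groups 3+4 count then runs from 1.58 to 12.91 of 50 over the three timings.

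These are admissions, not conflict cases. Deaths, transplants, refusals and FMT-related events, where both rules withhold the dose, would subtract. OHE without admission, fever, GI and laboratory triggers would add.

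**The case against.** The best defence is a sequence: halt, adjudicate, then apply the Visit 4 list. Halting is not defined for individuals, and the study-level rules in the same part of the protocol start with a temporary suspension. Assessment of Causality sends SAEs to a panel that votes on relatedness, and exception (c) turns on that vote. Visit 4 is also the more specific text on the second dose. This is a sensible way to run the trial, but it is not written anywhere, and it does not fit the word withdrawn, which the protocol uses both after the halting list and under Health risks. It shows what the fix should say; it does not show that the plan already says it.

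A reader might take the Visit 3 condition, "If no adverse event (AE) or serious adverse events (SAE) occur", as a third rule ending participation. It is weak support. The text does not say that a subject with an event stops, and read strictly any mild AE would end participation, which contradicts the graded thresholds elsewhere. The point does not rely on it.

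A reader might also infer that halted subjects are lost to the interim assessments. The monthly follow-up paragraph, which covers samples, cognitive tests and QOL, follows every patient for 6 months despite an SAE or hospitalization. It names only death, transplant and withdrawal of consent as reasons to stop. The reference to safety in the halting section does not clearly override that. What remains is narrow: the assessment one month after the second intervention has no date when that dose is withheld.

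**Conclusion.** The conflict is real and should be fixed. It covers fever with signs of infection, SAEs, OHE and non-elective admissions before day 30 that are not FMT-related, and it leaves rules 2, 5 and 6 without a counterpart at Visit 4. This rests on the text alone, plus reading an individual halt as a stop to study product, which the sentence closing the halting list supports.

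The size is illustrative: roughly 4 to 9 of 100 subjects hospitalized by day 30 at the plan's rates, with more in the placebo-capsule groups under all three assumed timings.

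Two stronger conclusions are tempting and unsupported. One is that the primary endpoint is compromised: the 6-month safety follow-up and the End-of-Study assessments continue whichever rule is applied. The other is that secondary aim 5 (microbiota after the second oral dose) is biased by selective dosing. That would follow only if the analysis were limited to second-dose recipients. No text limits it so, and the plan compares all outcomes between groups.

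**What to change.** State one second-dose rule in Visit 4 and conform the individual halting rules and Health risks text to it.

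- After an SAE, OHE episode, infection or hospitalization, let exceptions (a) to (d) govern. Exception (c) and the deferral provisions already turn on relatedness.
- Hold the dose until adjudication is complete, in the same way in all four groups. The DMC meets three times a year and the only delay now foreseen runs to day 45, so say how a vote is obtained in time and what happens if it is not.
- Add rules 2, 5 and 6 to the Visit 4 list as reasons to withhold, so that those safety stops are kept.
- Replace withdrawal from the study with *no further study product*, consistent with the 6-month follow-up of every patient.
- Date the post-second-dose assessment at day 60 (day 30 plus one month) for undosed subjects.

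The cost is a protocol amendment with the usual IRB and FDA review, and some added delay to second doses awaiting adjudication. No new visit type or test is needed.

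### The individual halting rules and the follow-up schedule conflict on whether assessments continue after an SAE, overt HE or hospitalisation, so cognition, quality-of-life and microbiota data may be lost unequally by arm

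*Combined protocol and SAP*

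**What the plan says.** The protocol addresses what happens after an adverse outcome in four places.

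- **Procedures, Visit 3.** Continuing in the study is worded as a condition: "If no adverse event (AE) or serious adverse events (SAE) occur", the subject goes on.
- **Individual study halting rules.** Rule 4 reads "SAE development including cirrhosis complications (OHE) and hospitalizations for" any cause, and the last rule is "7) Non-elective Hospitalization". Other rules cover GI symptoms, fever with signs of infection, MELD and liver enzymes. None has a time limit. The list closes with "Even if the subject is withdrawn before 30 days, they will still be followed till 6 months for safety".
- **Health risks.** For confirmed fever, an investigation is "performed as part of standard clinical care and the patient will be withdrawn from the study". A change of magnitude 3 in diarrhoea and cramps has the same consequence.
- **Follow-up visits every month.** "We will continue to follow every patient for 6 months regardless of whether they developed an SAE or hospitalization in between". The next sentence is exhaustive: "Only reasons not to follow them up for 6 months would be death, liver transplantation or patient withdrawal of consent". This follow-up includes sample collection, and "We will also perform the cognitive tests and QOL assessment at one month post-second intervention and at 6 months". The End-of-Study visit adds serum and stool.

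The Statistical analysis paragraph compares changes by ANOVA, adjusted for age, gender, MELD and alcoholic etiology. It gives no analysis population and no method for missing data.

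**The concern.** The halting triggers are the trial's own outcomes. HE recurrence is part of the primary endpoint, and hospitalisation is the outcome on which the sample size rests. If meeting a trigger ended assessment, the patients who did badly would drop out of the cognitive, quality-of-life and microbiota comparisons. If FMT works, more of them would drop out of placebo than of the FMT arms. The remaining placebo patients would be a low-risk selection, which works against FMT. Adjusting an ANOVA of changes for baseline covariates does not undo loss triggered by an event after randomisation, and data never collected cannot be recovered at analysis.

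**Working it through.** **Does halting mean only stopping product?** Product is given at baseline and at day 30 (up to day 45 if delayed). The halting rules have no time limit. After the second dose no product is left to stop, so a halt at that stage could affect only assessments. Before the second dose, Visit 4 has its own conditions for withholding it. For SAEs these cover only events adjudicated as FMT-related, and patients with an FMT-unrelated infection are approached again after antibiotics. Neither condition matches the any-SAE rule or the fever and infection rule. The text therefore does not settle what halting means.

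**Plan's rates and stated power.** The Sample size paragraph gives 6-month hospitalisation of 10% (dual), 30% (rectal alone), 30% (oral alone) and 80% (standard of care). A four-group chi-square test with 3 df at α = 0.05 has noncentrality λ = n·Σ(p − p̄)²/[p̄(1 − p̄)], with p̄ = 0.375. At n = 25, λ = 25 × 0.2675/0.2344 = 28.5.

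| n per group | Power computed | Power stated |
|---|---|---|
| 25 | 99.7% | 100% |
| 20 | 98.8% | 98% |
| 15 | 94.9% | 94% |

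The rates are thus read as the plan intends. This power is for hospitalisation itself and is not affected by the point made here.

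**Worst-case retention at month 6.** Assume that every hospitalised subject gives no further assessments. Retained n = 25(1 − p), which is 22.5, 17.5, 17.5 and 5 in Groups 1 to 4. The expected loss is 37.5 of 100.

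**Bias, Group 1 v Group 4, completers only.** Assume a standard normal liability to hospitalisation, with threshold z set so that a proportion p exceeds it. The outcome correlates ρ with liability and there is no true treatment effect on it. Retained subjects in an arm are shifted by ρ·φ(z)/(1 − p) toward the healthy side.

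- Placebo, p = 0.8: 0.280/0.2 = 1.400.
- Dual FMT, p = 0.1: 0.1755/0.9 = 0.195.
- Difference: 1.205ρ, which is 0.24, 0.48 and 0.72 SD in favour of placebo at ρ = 0.2, 0.4 and 0.6.

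The standard error relative to 25 v 25 is √(1/5 + 1/22.5)/√(2/25) = 1.75. The difference detectable with 80% power, (1.96 + 0.84)·√(1/n₁ + 1/n₂), rises from 0.79 SD to 1.39 SD.

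**Earlier assessments.** Assume a constant hazard over 180 days, so the proportion lost by day d is 1 − (1 − p)^(d/180).

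| Day | Lost, placebo / dual | Retained, placebo v dual | Bias at ρ = 0.2, 0.4, 0.6 (SD) | SE ratio |
|---|---|---|---|---|
| 30 | 23.5% / 1.7% | 19.1 v 24.6 | 0.07, 0.14, 0.21 | 1.08 |
| 60 | 41.5% / 3.5% | 14.6 v 24.1 | 0.12, 0.24, 0.35 | 1.17 |
| 180 | 80% / 10% | 5 v 22.5 | 0.24, 0.48, 0.72 | 1.75 |

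**Under the monthly follow-up section.** Loss from this cause is 0 in every arm.

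**The case against.** The strongest reply is that the follow-up section already answers the point. It is specific, gives an exhaustive list of reasons to stop, and schedules the very assessments at issue. The closing sentence of the halting rules can be read as an added reassurance, not as a list of what stops. Explicit withdrawal from the study is written only for confirmed fever and the GI change, not for overt HE, SAEs or hospitalisation.

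Much of this stands. A reader might infer that halted subjects are followed for safety alone, and that their cognitive, quality-of-life and stool data will certainly be lost. The documents do not support that. They never say that follow-up is limited to safety, and the sentence concerns subjects withdrawn before day 30. Nor do they support a claim that the primary endpoint is lost: SAE and hospitalisation follow-up is largely kept under either reading.

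The size is also a worst case. It takes the most extreme pair of arms at the latest time point. The 80% is a standard-of-care rate from an earlier trial with 10 per group, applied here to placebo. The correlations are assumed. Each single-route arm would itself lose 7.5 of 25, so it would be wrong to say that the FMT arms stay nearly complete.

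The reply does not remove the conflict. The Visit 3 condition, the untimed halting rules and the withdrawal wording remain beside the follow-up section, and no text says which applies to outcome collection.

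**Conclusion.** The point holds as an internal contradiction with a conditional consequence, and should be fixed. The Visit 3, halting-rule and Health risks text conflicts with the monthly follow-up section on what happens after the trial's own outcome events. The exposure is confined mainly to secondary aims 2, 3 and 5.

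If halting is applied as withdrawal from assessments, the completers-only bias against dual FMT runs from about 0.07–0.21 SD at day 30 to 0.24–0.72 SD at month 6. This rests on the plan's hospitalisation rates, a normal liability, correlations of 0.2 to 0.6 and, before month 6, a constant hazard. The upper figures bound the hospitalisation trigger alone; loss from the fever, GI and laboratory triggers is not counted. If the follow-up section is applied, the loss is zero. These figures show what the ambiguity could cost and do not predict the trial's result.

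**What to change.** Reconcile the sections for outcome collection only.

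1. State under Visit 3, Individual study halting rules and Health risks that meeting a halting rule does not end outcome collection.
2. State that Visit 4, the assessment one month after the second dose (or at its scheduled time if no second dose is given) and Month 6 are done in every consenting subject. These comprise PHES, EncephalApp, SIP and the samples already scheduled at each visit.
3. State that all subjects are analysed in their randomised group, and how values still missing after death, transplantation or withdrawal of consent are handled.
4. Replace the closing sentence of the halting rules to match, so that it is limited neither to withdrawal before day 30 nor to safety.

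The Visit 4 conditions for the second dose also conflict with the halting rules. The clinical team must reconcile them, and no rule is proposed here. For that reason the amendment should not simply declare that the Visit 4 and follow-up text prevails, since that would also settle the dosing question.

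The cost is protocol wording and a short analysis statement. The assessments are already scheduled for all 100 patients; the documents give no budget from which to price visits by subjects who would otherwise have been treated as withdrawn. The change must be made while follow-up can still take place.
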